3.1 Trial Design

This observer-blind, randomized, Phase II non-inferiority trial will be conducted in 2 sequential stages.

At enrollment, for STAGE I, approximately 1050 healthy subjects between 9 and 50 years of age will be randomized (1:1:1) stratified by site (████, █████, █████, ██████████, █████ and █████) and age group (Children 9-11 years, Adolescents 12-17 years, Adults 18-39 years and Adults 40-50 years) to 1 of 3 treatment arms (Groups 1, 2, or 3) to receive 3 injections (in various schedules of CYD dengue vaccine and placebo administration) over a 12-month period (administered 6 months apart: at D0; D0 + 6 months; and D0 + 12 months).

For STAGE II, subjects randomized to each of the 3 treatment arms in STAGE I will also be randomized (1:1) to 1 of 2 subgroups (e.g., subgroup a or b). The subject's dengue serostatus at baseline, based on plaque reduction neutralization test (PRNT), will determine her/his eligibility to receive the booster injection. Only the subjects identified as dengue seropositive at baseline will receive a booster injection of CYD dengue vaccine at either 12 months (Subgroup a, Injection 3 + 12 months) or 24 months (Subgroup b, Injection 3 + 24 months) following the last primary series injection.

At each injection visit in STAGE I, subjects will receive a single dose of either CYD dengue vaccine (CYD) or placebo (PLA): Group 1 subjects (N = 350) will receive CYD dengue vaccine at all 3 injection visits; Group 2 subjects (N = 350) will receive PLA at the first injection visit and CYD dengue vaccine at the last 2 visits; and Group 3 subjects (N = 350) will receive PLA at the first 2 visits and CYD dengue vaccine at the last injection visit.

A total of 60 subjects (10 subjects in each of 6 subgroups) who consent to participate in additional immunological testing will also be included in a specific subset (AIT subset). It is to be noted that the 1:1 ratio per subgroup is unlikely to hold as only subjects dengue seropositive at baseline will be eligible to booster injection.

Blood samples will be taken at several time points throughout the study for CMI, neutralizing Ab, and Ab specificity and affinity maturation assessments. More details are provided in Section 5.1.3 of the protocol.

The duration of each subject's participation in the trial will be approximately 30 to 42 months.

3.2 Trial Plan

STAGE I

Before inclusion, the Investigators will inform potentially eligible subjects and / or their parents / legally accepted representative(s) about the trial and will give them an oral description of the trial design, with the general risks and benefits that have been associated with the trial and the injections. Then, each subject / subjects' parent(s) / legally acceptable representative(s) will sign and date consent forms (informed consent form [ICF] and assent form [AF], as applicable). An

interactive voice response system / interactive web response system (IVRS/IWRS) will be used to assign treatment groups and subject numbers at each clinic site.

Vaccination

All subjects (N=1050) will receive 1 injection at D0, D180 and D365: a total of 350 subjects will receive 3 doses of CYD dengue vaccine (Group 1); 350 subjects will receive 1 PLA injection followed by 2 doses of CYD dengue vaccine (Group 2); and 350 subjects will receive 2 PLA injections followed by 1 dose of CYD dengue vaccine (Group 3).

Blood Sampling

All subjects will provide a blood sample (BL) at enrollment V01 (pre-Injection 1, BL1), at V03 (pre-Injection 2, BL2) at V04 (V03 + 28 days, BL3), at V05 (pre-Injection 3, BL4), at V06 (V05 + 28 days, BL5), and at Y1 V07 (V05 + 12M, BL6) for dengue immunogenicity

Safety Data Collection

Reactogenicity data will be collected in all subjects after the CYD or PLA injection: solicited injection site reactions will be collected for Days 0–7; immediate adverse events (AEs) observed to occur within 30 min post-injection will be collected; solicited systemic reactions will be collected for Days 0–14; and unsolicited non-serious events will be collected for Days 0-28.

In addition, hospitalized suspected dengue cases occurring at any time in the trial will be documented. Hospitalized suspected dengue disease is defined as an acute febrile illness with a diagnosis of dengue requiring hospitalization (with bed attribution).

Serious adverse events (SAEs) will be reported throughout the study and serious and non-serious AESIs will be collected in defined time-windows according to the type of AESI.

STAGE II

Vaccination

Before the beginning of STAGE II, blood samples collected before the first injection of CYD dengue vaccine (at V01 for Group 1, V03 for Group 2, and V05 for Group 3) will be used for determining the baseline dengue serostatus for study participants in order to determine if booster injection can occur during STAGE II. Only subjects identified as dengue seropositive will be eligible to receive the booster injection. Dengue serostatus will be determined using the Dengue PRNT assay. A “seropositive” subject has been generally defined by a PRNT 50 titer $\geq 1:10$ to any dengue serotype at baseline, and a “seronegative” subject has been defined by a PRNT 50 titer <10 for all four dengue serotypes.

At 1 year following the last primary series vaccination, subjects dengue seropositive at baseline from subgroup a (1a, 2a, and 3a) will receive a single booster dose of CYD dengue vaccine. At 2 years following their last primary series vaccination, dengue seropositive in subgroup b (1b, 2b, and 3b) will receive a single booster injection of CYD dengue vaccine

Blood Sampling

Each STAGE II subject will provide blood samples for assessing neutralizing Ab titers against each of the 4 parental dengue virus strains immediately before and 28 days after receiving the booster injection

Safety Data Collection

For all STAGE II subjects, reactogenicity data will be collected in all subjects after the CYD injection: immediate adverse events (AEs) observed to occur within 30 min post-injection will be collected; solicited injection site reactions will be collected for Days 0–7; solicited systemic reactions will be collected for Days 0–14; and unsolicited events will be collected for Days 0–28.

In addition, hospitalized, suspected dengue cases occurring at any time in the trial will be documented. Hospitalized suspected dengue disease is defined as an acute febrile illness with diagnosis of dengue requiring hospitalization (with bed attribution).

SAEs will be reported throughout STAGE II (and 6-month follow-up following booster injection) and serious and non-serious AESIs will be collected in defined time windows according to the type of AESI. Safety will also be followed up until 6 months after V07 for booster Y1 and for booster Y2

STAGE I and STAGE II

Additional Immunological Tests (AIT) Subset

In addition to the blood samples described above, samples will also be drawn from 60 subjects from a specific site in Colombia who consent to participate in the AIT subset.

For evaluations of CMI Ab specificity and affinity maturation, blood samples will be taken from STAGE I subjects immediately before Injection 1 (specificity, affinity and CMI) and at 28 days following injection 3 (specificity and affinity).

During STAGE II, only subjects identified as seropositive at baseline and thus eligible to booster injection will continue to be part of the AIT subset. The sampling from these subjects will continue into STAGE II when samples will be drawn immediately before the booster injection, and at 7 days, 14 days, and 28 days post-booster injection for Ab specificity and CMI; Ab affinity maturation will be assessed only prior to and 28 days post-booster injection.

See Table 3.1 for details of study procedures

Table 3.1: Study procedures

Table of Procedures – STAGE I and STAGE II

Visit Number (V)	STAGE I							STAGE II*								
	V01	V02	V03	V04	V05	V06	6M FU (PC7)†	V06-Inf	V07 (Y1)	V07 (Y2)	V08 (Y1/Y2) (AIT only)	V09 (Y1/Y2) (AIT only)	V10 (Y1/Y2)	6M FU (PC)‡		
Trial timelines (Days/Months)	V01	V01+ 28d	V01+ 180d	V03+ 28d	V01+ 365d	V05+ 28d	last inj + 6M		V05+ 12M	V05+ 24M	V07+ 7d	V07+ 14d	V07+ 28d	V07+ 6M		
Time Windows (Days)		+14d	±20d	+14d	±20d	+14d	+20d		+60	+60	+3d	+7d	+14d; +7d AIT only)	+20d		
Informed Consent/Assent	√								√							
Information letter on baseline serostatus								√								
Inclusion/Exclusion Criteria	√															
Demography	√															
Contraindications	√		√		√				Subgroup a: V07 Y1 Subgroup b: V07 Y2							
Significant Medical History	√															
History of YF or JE Infection/Vaccination and/or Dengue Infection	√															
Physical Examination and Temperature§	√	√	√	√	√	√			subgroup a: V07 Y1 subgroup b: V07 Y2		√	√	√			
Urine Pregnancy Test (pre-injection)**	√		√		√											
Concomitant Therapy	√	√	√	√	√	√							√	√	√	
IVRS/IWRS Contact	√		√		√											
Injection	Inj. 1		Inj. 2		Inj. 3				Booster Inj. subgroup a: V07 Y1 subgroup b: V07 Y2							

STAGE I								STAGE II*						
Visit Number (V)	V01	V02	V03	V04	V05	V06	6M FU (PC7)†	V06-Inf	V07 (Y1)	V07 (Y2)	V08 (Y1/Y2) (AIT only)	V09 (Y1/Y2) (AIT only)	V10 (Y1/Y2)	6M FU (PC)‡
Trial timelines (Days/Months)	V01	V01+ 28d	V01+ 180d	V03+ 28d	V01+ 365d	V05+ 28d	last inj + 6M		V05+ 12M	V05+ 24M	V07+ 7d	V07+ 14d	V07+ 28d	V07+ 6M
Time Windows (Days)		+14d	±20d	+14d	±20d	+14d	+20d		+60	+60	+3d	+7d	+14d; +7d AIT only)	+20d
Blood Sampling††	BL1		BL2	BL3	BL4	BL5			BL6 (all subjects)	BL10 (subgroup b only)			BL9 or BL13‡‡	
30-min observation period	√		√		√				subgroup a: V07 Y1 subgroup b: V07 Y2		√	√	√	
Injection site reactions & systemic events§§	√	√	√	√	√	√								
Diary Card (DC): Provided:	DC1		DC2		DC3				DC4 or DC4 Group b or MA2	DC5				
Checked and/or collected:		DC1		DC2		DC3			***	DC4 Group b ***	DC4/DC5	DC4/DC5	DC4/DC5	
Memory Aid (MA): Provided:						MA1								
Checked:							MA1		MA1				MA2	MA2
Termination Record													√	
SAEs and Serious AESIs†††	To be reported throughout the study period													
THE FOLLOWING ADDITIONAL PROCEDURES APPLY ONLY TO THE AIT SUBSET														
Additional neutralizing Ab											BL7 or BL11‡‡	BL8 or BL12‡‡		
Affinity maturation and specificity assays	BL1					BL5			BL6‡‡	BL10‡‡	BL7 or BL11‡‡ ‡‡‡	BL8 or BL12‡‡ ‡‡‡	BL9 or BL13‡‡	

STAGE I							STAGE II*							
Visit Number (V)	V01	V02	V03	V04	V05	V06	6M FU (PC7)†	V06-Inf	V07 (Y1)	V07 (Y2)	V08 (Y1/Y2) (AIT only)	V09 (Y1/Y2) (AIT only)	V10 (Y1/Y2)	6M FU (PC)‡
Trial timelines (Days/Months)	V01	V01+ 28d	V01+ 180d	V03+ 28d	V01+ 365d	V05+ 28d	last inj + 6M		V05+ 12M	V05+ 24M	V07+ 7d	V07+ 14d	V07+ 28d	V07+ 6M
Time Windows (Days)		+14d	±20d	+14d	±20d	+14d	+20d		+60	+60	+3d	+7d	+14d; +7d AIT only)	+20d
CMI	BL1								BL6‡‡	BL10‡‡	BL7 or BL11‡‡	BL8 or BL12‡‡	BL9 or BL13‡‡	

NAb: neutralizing antibodies; CMI: cellular mediated immune response; Aff: affinity; AIT: Additional Immunological Testing subset.

- * As describe in the synopsis, dengue seronegative subjects at baseline will attend Y1 V07 and have the possibility to provide BL6 once having consented to continue in the trial. After the Y1 V07, they will no longer have to come back to the site.
- † See Table of procedures (Phone Contacts). Subjects having prematurely terminated the trial will be contacted by phone for the 6-month safety follow-up.
- ‡ See Table of procedures (Phone Contacts). Subjects eligible to booster injection will be contacted by phone for the post-booster injection 6-month safety follow-up (PC12 for subjects from subgroup a and PC15 for subjects from subgroup b). Subjects non-eligible to booster injection will be contacted by phone as part of the safety follow-up.
- § Axillary temperature will be obtained for vaccination visits; also, note that febrile illness on the day of vaccination is a temporary contraindication.
- ** Urine pregnancy test for females of child-bearing potential; to be considered of non-child-bearing potential, a female must be post-menopausal for at least 1 year, surgically sterile, or using an effective method of contraception or abstinence from at least 4 weeks prior to vaccination and until at least 3 weeks after vaccination
- †† Blood samples planned during vaccination visits will be taken before injection. Baseline YF and JE status will be assessed using PRNT.
- ‡‡ BL6 is to be taken in all subjects 1 year after last injection (at V05 + 12M). BL10 is to be taken in subjects from subgroup b 2 years after last injection (at V05 + 24M). BL7 through BL9 are taken in subgroup a only; and BL11 through BL13 are taken in subgroup b only.
- §§ Solicited injection site reactions will be collected for 7 days after injection. Solicited systemic reactions will be collected for 14 days after injection. Unsolicited AEs will be collected for 28 days after injection.
- *** DC4 will be provided to subgroup a to collect the full safety information after booster injection at Y1. DC4 Group b will be provided to subgroup b to collect SAEs from V07 Y1 to V07 Y2. DC5 will be provided to subgroup b to collect full safety information after booster injection at Y2. Dengue seronegative subjects at baseline from both subgroups will be provided with MA2.
- ††† Serious AESIs will be reported after each injection in defined time windows as follows: serious hypersensitivity/allergic reactions occurring within 7 days, serious viscerotropic disease occurring within 30 days, serious neurotropic disease occurring within 30 days; hospitalized suspected dengue disease will be reported during the entire study. Non-serious AESIs (ie, hypersensitivity / allergic reactions) will be reported within 7 days after each injection.
- ‡‡‡ At these time points, Ab specificity may be assessed, if necessary; Ab affinity maturation will not be assessed.

Table of Procedures – Phone Contacts

	STAGE I									STAGE II					
Phone Contact (PC)	PC1	PC2	PC3	PC4	PC5	PC6	PC7*	PC8	PC9	PC10	PC11	PC12*	PC13†	PC14†	PC15†
Trial timelines (Days/Months)	V01+ 2M	V01+ 4M	V01+ 8M	V01+ 10M	V01+ 14M	V01+ 16M	V01+ 18M	V01+ 20M	V01+ 22M	V05 + 14M	V05 + 16M	V05 + 18M	V05 + 20M	V05 + 22M	V05 + 30M
Time Windows (Days)	+8d	+8d	+8d	+8d	+8d	+8d	+20d	+8d	+8d	+8d	+8d	+8d	+8d	+8d	+20d
Ask about SAEs not yet reported‡	√	√	√	√	√	√	√	√	√	√	√	√	√	√	√
Remind subject / parent / legal acceptable representative to notify the site in case of an SAE	√	√	√	√	√	√	√	√	√	√	√	√	√	√	√
Review MA§ subgroup a subgroup b					MA1	MA1	MA1	MA1	MA1	DC4 or MA2	DC4	DC4			
					MA1	MA1	MA1	MA1	MA1	DC4 Group b or MA2	DC4 Group b	DC4 Group b	DC4 Group b	DC4 Group b	MA2

* At PC7, all subjects will receive a post-Injection 3 safety follow-up phone call. At PC12, subgroup a subjects will receive the post-booster injection safety follow-up phone call, while subjects in subgroup b will receive a standard phone call from the study center.

† PC13 to P15 will be made only for subgroup b subjects. PC15 will be subgroup b post-booster injection safety follow-up phone call

‡ If an SAE occurred, instructions in [Section Error! Reference source not found.](#) for reporting are to be followed

§ Review information entered into MA by interviewing subject / subject's parent(s) / legally acceptable representatives and request information concerning any medical event serious or not, that may have occurred since Visit 6

4 Endpoints and Assessment Methods

4.1 Primary Endpoints and Assessment Methods

4.1.1 Immunogenicity

4.1.1.1 Immunogenicity Endpoints

See Section 9.1.1.1 of the protocol.

4.1.1.2 Immunogenicity Assessment Methods

See Section 9.1.1.2 of the protocol.

4.1.2 Safety

There are no primary objectives for safety.

4.1.3 Efficacy

No clinical efficacy data will be obtained in the trial.

4.2 Secondary Endpoints and Assessment Methods

4.2.1 Immunogenicity

4.2.1.1 Immunogenicity Endpoints

See Section 9.2.1.1 of the protocol.

4.2.1.2 Immunogenicity Assessment Methods

See Section 9.2.1.2 of the protocol.

4.2.2 Safety

4.2.2.1 Safety Endpoints

See Section 9.2.2.2 of the protocol.

4.2.2.2 Safety Assessment Methods

See Section 9.2.2.3 of the protocol.

4.2.3 Efficacy

No clinical efficacy data will be obtained in the trial.

4.3 Additional Endpoints and Assessment Methods

4.3.1 Immunogenicity

4.3.1.1 Immunogenicity Endpoints

See Section 9.3.1.1 of the protocol.

4.3.1.2 Immunogenicity Assessment Methods

See Section 9.3.1.2 of the protocol.

The lower limit of detection (LLOD) for the 50% of neutralization titer by flow cytometry for Ab specificity is a titer of 20. To be able to calculate affinity, the LLOD for measuring the kinetic rates is an Ab concentration of 1 ng/mL and the lowest dissociation constant K_D that can reliably be measured on the instrument is 10 pM.

4.3.2 Safety

There are no additional objectives for safety.

4.3.3 Efficacy

No clinical efficacy data will be obtained in the trial.

4.4 Derived Endpoints: Calculation Methods

4.4.1 Immunogenicity

4.4.1.1 Computed Values for Analysis

For the computation of GMTs, a titer reported as < LLOQ will be converted to a value of 0.5 LLOQ.

For calculating geometric mean titer ratio (GMTR), < LLOQ will be converted to 0.5 LLOQ for a numerator and < LLOQ will be converted to LLOQ for a denominator

Any titer reported as > upper limit of quantification (ULOQ) will be converted to ULOQ.

4.4.1.2 Seroconversion

If a pre-booster titer < 10 (1/dil) and a post-booster dose titer is ≥ 40 (1/dil) then the derived seroconversion indicator will be “Yes” for that test. Or, if a subject has a pre-booster titer ≥ 10 (1/dil) and achieves ≥ 4 -fold increase from pre to post-booster dose titer then the seroconversion indicator will be “Yes” for the test. Otherwise, seroconversion will be “No”.

4.4.1.3 Calculation rules for the “at least X serotype(s)” tables

The criteria below will be computed for each subject and visit as soon as at least one of the four dengue serotype result is different from missing or not-reportable (NR) (i.e. coded no result in the serology database):

- Number and percentage of subjects with antibody titer ≥ 10 (1/dil) against at least 1, 2, 3, or 4 serotypes with the parental dengue virus strains.
- Number and percentages of subjects with antibody titer \geq various titer thresholds (1/dil) against at least 1, 2, 3, or 4 serotypes with parental the dengue virus strains.

Titer(s) \geq to a threshold for at least X serotype(s) with parental dengue virus strains is computed as a Yes/No/Missing variable (note: in the case no titer is available the variable will be missing). If at least X among the 4 serotype titers meet the threshold considered then the variable is derived to “Yes”, otherwise if at least one titer is available and does not meet the threshold the variable is derived to “No”. For the percentage calculation, all the subjects with at least one titer available regardless of the serotype will be considered in the denominator.

4.4.1.4 Flavivirus, Dengue and Yellow Fever/Japanese Encephalitis status

4.4.1.4.1 Baseline flavivirus (FV) status

Flavivirus (FV) status at baseline is defined as

- **Immune** for subjects with quantified (\geq LLOQ) neutralizing Abs against Japanese Encephalitis (JE), Yellow Fever (YF), and/or against at least one dengue serotype in the baseline sample.
- **Non-immune** for subjects without quantified ($<$ LLOQ) neutralizing Abs against JE, YF and with no Ab quantified against any of the four dengue serotypes in the baseline sample. To be classified in this group, *all* of the titers planned to be measured at baseline must be *available*, and *valid* i.e., not coded 'NR' in the serology database, otherwise the FV status will be classified as "*undetermined*."

The FV status will be **undetermined** for subjects that have a value $<$ LLOQ and/or ‘missing’ and/or ‘NR’ results for all of the FVs planned to be measured. This category will not be presented separately but will be included in the ‘All subjects’ category.

The LLOQ for dengue, JE and YF neutralizing Abs is 10 (1/dilution [dil]).

4.4.1.4.2 Baseline Dengue Status

The dengue status at baseline is defined as the presence of Abs against at least one dengue serotype in the baseline blood sample. The baseline dengue blood sample closest to the first injection of CYD dengue vaccine will be assayed in priority as follows:

- Group 1 baseline dengue sample is the blood sample collected at V01 (BL1)
- Group 2 baseline dengue sample is the blood sample collected at V03 (BL2, or BL1 if BL2 is unavailable)

- Group 3 baseline dengue sample is the blood sample collected at V05 (BL4, or BL2 if BL4 is unavailable, or even BL1 if BL2 is unavailable)

The baseline dengue status variable will be calculated as follows:

- Immune for subjects with quantified (\geq LLOQ) neutralizing Abs against at least one dengue serotype in the baseline sample.
- Non-immune for subjects with no quantified ($<$ LLOQ) neutralizing Abs against all of the four dengue serotypes in the baseline sample. In this group, all of the titers planned to be measured at baseline must be available and, valid i.e., different from no result ('NR') in the serology database, otherwise the baseline dengue status will be classified as "undetermined".

The baseline dengue status will be undetermined for subjects that have 'missing' and/or 'NR' results for all of the four dengue serotypes measured at baseline and for subjects who have values $<$ LLOQ for some serotypes and a combination of 'missing' and 'NR' results for all others of the four dengue serotypes measured at baseline. Baseline dengue status will be used to identify the status of subjects at baseline.

4.4.1.4.3 Baseline Yellow Fever and Japanese Encephalitis Status

The following baseline statuses with identical categories as baseline dengue status (i.e., immune, non-immune and undetermined) are defined as follows:

- Baseline JE status for subjects in the Philippines: considering neutralizing Abs against JE
- Baseline YF status for subjects in Colombia: considering neutralizing Abs against YF

The baseline blood sample used for YF and JE status is at V01 (BL1) for all subjects.

4.4.2 Safety

Terms used in the clinical safety tables to describe the safety events are specified below:

- AE: Adverse event; includes immediate, solicited, and unsolicited non-serious or serious adverse events.
- AR: Adverse reaction; Adverse reaction corresponds to related AE
- Immediate AE/AR: Unsolicited non-serious AE ticked "immediate (within 30 minutes from the vaccination)" by the investigator in the eCRF or SAE with time of onset within 30 minutes
- Solicited reaction: Event pre-listed in the eCRF, and which occurred during the solicited period (period is 0 to 7 days for injection site reactions and 0 to 14 days for systemic reactions post-vaccination)
- Unsolicited AE: AE recorded in the eCRF unsolicited form and SAE form, excluding solicited reactions. Therefore, this term includes immediate AEs/ARs.
- Unsolicited non-serious injection site events are always recorded without relationship and analyzed as ARs.
- SAE: Unsolicited AE considered serious by the investigator.

- Hospitalized suspected dengue case: Hospitalized suspected dengue disease is defined as an acute febrile illness with diagnosis of dengue requiring hospitalization (with bed attribution).
- VCD case: A VCD infection is defined as a suspected dengue which has positive sample for the dengue screen RT-PCR (i.e., \geq LLOQ) and/or the non-structural protein 1 (NS1) antigen (Ag) enzyme-linked immunosorbent assay (ELISA) is positive and/or the Simplexa™ dengue reverse transcription-polymerase chain reaction (RT-PCR) is positive. Dengue NS1 Ag ELISA positive is defined as sample ratio >1 by comparing the optical density reading of the sample to the optical density of the cutoff control serum. The Simplexa™ Dengue RT-PCR positive is defined as detected results for at least one dengue serotype.

4.4.2.1 Solicited Reactions

4.4.2.1.1 Daily Intensity

All daily records for solicited reactions will be derived into daily intensity according to the following classification: None, Grade 1, Grade 2, Grade 3, or Missing.

For the derivation of daily intensities the following sequential steps will be applied:

- 1) Solicited reactions (except Fever/Pyrexia) with an investigator presence recorded as “No” and with all daily records missing then all daily intensities will be derived as None.
- 2) For non-measurable solicited reactions, daily intensities will correspond to daily records reported in the clinical database. For measurable solicited reactions the daily measurements reported in the clinical database will be converted based upon the intensity scales defined in Section 9.2.2.3.2 of the protocol; this assumes a reaction that is too large to measure (non measurable, [NM]) is Grade 3. Note the intensity could be considered as “None” (i.e., not a reaction) in the analysis despite being considered a reaction by the Investigator (e.g., Injection site swelling measurement > 0 mm and < 25 mm in adolescents or adults).

Note: The maximum intensity on the ongoing period is derived from the record of the maximum intensity/measurement after the end of the solicited period following the rule described above.

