13.2 Source Data and Source Documents

“Source data” are the data contained in source documents. Source documents are original documents or certified copies, and include, but are not limited to, DCs, MAs, medical and hospital records, screening logs, ICFs / AFs, telephone contact logs, and worksheets. The purpose of trial source documents is to document the existence of subjects and to substantiate the integrity of the trial data collected. Investigators must maintain source documents so that they are accurate, complete, legible, and up to date.

For missing or discrepant data on a DC, the study coordinator or designee will obtain verbal clarification from the subject, enter the response into the "Investigator's comment" page of the DC, and transfer the information to the eCRF.

The subject pre-screening log should list all individuals contacted by the Investigators to participate in the trial, regardless of the outcome.

The Investigator must print^a any electronic records on an ongoing basis, sign and date them immediately after creation, and keep the printouts on file as source documents that can be verified by the Sponsor or an inspector against the electronic records. Any later changes of an electronic record require the record to be re-printed, dated (with an indication of the date of change), and signed. Such records must also be kept together with the original printed copy.

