4.4.2.1.3 Presence

Presence is derived from the maximum intensity on the period considered:

- None: No presence
- Grade 1, Grade 2, or Grade 3: Presence
- Missing: Missing presence

Subjects with at least one non-missing presence for a specific endpoint will be included in the analysis. Conversely, those without a non-missing presence will not be included in the analysis of the endpoint.

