4.4.2.1.7 Ongoing

Ongoing is derived from the last daily intensity of the solicited period computed as described in [Section 4.4.2.1.1](#) and the maximum intensity on the ongoing period. The investigator's ongoing flag is not used because the measurement would determine the ongoing status of the reaction. Note the intensity could be considered as "None" (i.e., not a reaction) in the analysis despite being considered a reaction by the Investigator (e.g., Injection site swelling measurement > 0 mm and < 25 mm in adolescents or adults).

If the last daily intensity of the solicited period is at least Grade 1 and maximum intensity on the ongoing period is also at least Grade 1, then the reaction is considered ongoing. In any other cases the reaction will not be considered as ongoing.

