5.3.2.4 Intensity

For solicited reactions, missing intensities will be handled as described in [Section 4.4.2.1.1](#). For unsolicited non-serious AEs, missing intensities will remain missing and will not be imputed.

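### SAP 4.4.2.1.1 counts an ungraded investigator 'No' as no reaction but drops an ungraded 'Yes', so rates for the five non-measured symptoms are too low whenever such records occur

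*SAP*

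**What the plan says.** SAP 4.4.2.1.1 assigns each day of a solicited reaction one of the classes "None, Grade 1, Grade 2, Grade 3, or Missing". It does so in two ordered steps.

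- Step 1 has this scope: "Solicited reactions (except Fever/Pyrexia) with an investigator presence recorded as" negative. Its further condition and its outcome read: "and with all daily records missing then all daily intensities will be derived as None".
- Step 2 covers everything else. For reactions that are not measured, "daily intensities will correspond to daily records reported in the clinical database". For measured ones, the recorded value is converted to a grade.

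Neither step mentions an investigator answer of 'Yes'. Maximum intensity is the largest daily intensity (4.4.2.1.2), and presence is read from that maximum (4.4.2.1.3). A Missing maximum gives Missing presence, and the consequence is stated: "Conversely, those without a non-missing presence will not be included in the analysis of the endpoint".

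The missing-data sections add nothing for this case. SAP 5.3.2 rules out replacement unless stated elsewhere, 5.3.2.3 leaves missing measurements as they are, and 5.3.2.4 points back: "For solicited reactions, missing intensities will be handled as described in" 4.4.2.1.1.

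Under 4.4.2.1.7 a reaction is ongoing only if the last-day grade and the maximum grade in the ongoing period are both at least 1. "In any other cases the reaction will not be considered as ongoing". The overall-days variable in 4.4.2.1.6 extends past the solicited period only for reactions judged ongoing.

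On incomplete diary cards, Protocol 13.2 says that "the study coordinator or designee will obtain verbal clarification from the subject" and that the answer goes into the eCRF.

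**The concern.** One source, the investigator's answer, is trusted when it is negative and set aside when it is positive. A subject known to have had headache, but with no graded day, disappears from the headache table. A subject known not to have had headache, with the same blank grid, stays in its denominator.

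The situation is foreseeable: step 1 itself presupposes an investigator answer with no daily records, and later verbal recall may establish that a symptom occurred without giving a grade for each day.

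The rule also sits oddly with the rest of the SAP. Missing causality is counted as related (5.3.2.2), and unsolicited events with a missing onset stay in the tables (4.4.2.2.4, 5.3.2.5). Here a missing detail removes a reported reaction.

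At stake is the description of reactogenicity after each injection and booster, which is a secondary safety endpoint. The ongoing rule raises a smaller matter: a blank is read as evidence that the reaction stopped.

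**Working it through.** **Figure to reproduce.** None. The documents state neither an expected reactogenicity rate nor a frequency of missing daily records. What follows checks the rule, with assumed inputs marked.

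**Following the rule for a non-measured symptom, all daily records blank**

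| Step | Investigator 'No' | Investigator 'Yes' |
|---|---|---|
| Daily intensity (4.4.2.1.1) | None on all days (step 1) | Missing on all days (step 2) |
| Maximum (4.4.2.1.2) | None | Missing |
| Presence (4.4.2.1.3) | No presence | Missing |
| In the denominator? | Yes | No |

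**Effect on the rate.** Let N be the subjects with a presence answer, k the true reactors, and u the reactors with 'Yes' and no daily record. The SAP reports (k-u)/(N-u); keeping them gives k/N. The shortfall is

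k/N - (k-u)/(N-u) = u(N-k)/[N(N-u)],

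which is positive whenever u>0 and k<N. 'No' subjects with blank records are retained either way and do not enter the difference.

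**Numbers.** N=350 is the planned group size (SAP 5.5). The true rate and u are assumptions.

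| True rate | u (share of 350) | SAP rate | Shift, points |
|---|---|---|---|
| 40% (k=140) | 1 (0.3%) | 139/349 = 39.83% | -0.17 |
| 40% | 7 (2.0%) | 133/343 = 38.78% | -1.22 |
| 40% | 18 (5.1%) | 122/332 = 36.75% | -3.25 |
| 10% (k=35) | 1 (0.3%) | 34/349 = 9.74% | -0.26 |
| 10% | 7 (2.0%) | 28/343 = 8.16% | -1.84 |
| 10% | 18 (5.1%) | 17/332 = 5.12% | -4.88 |

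**Erythema and swelling.** From age 12 a size under 25 mm is graded None (SAP 4.4.2.1.1; Protocol Table 9.1), so an unmeasured 'Yes' might have been None had it been measured. Let q be the share of such cases that would have reached 25 mm. With 34 reactors among 343 retained subjects (9.91%) and u=7, the rate with those cases included is (34+7q)/350:

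- q=0: 9.71%, so the SAP rate is 0.2 points too high
- q=0.1: 9.91%, no difference
- q=0.5: 10.71%, so 0.8 points too low
- q=1: 11.71%, so 1.8 points too low

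The sign depends on q. At ages 9 to 11 any size above 0 mm is at least Grade 1, so there the direction is downward.

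**Ongoing rule.** Take injection-site pain from D5 to D20 with the ongoing-period grade missing. The last-day grade is at least 1 but the other grade is blank, so 4.4.2.1.7 makes it not ongoing, and only D5, D6 and D7 count: 3 days. Judged ongoing, the 4.4.2.1.6 formula with a solicited period of 8 days (D0 to D7) gives 20 + 3 - 8 + 1 = 16 days, which matches D5 to D20 counted inclusively. The solicited-period count in 4.4.2.1.5 is 3 days either way.

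**The case against.** The strongest reply is that this may hardly ever happen. Sites clarify incomplete diary entries (Protocol 11.1 and 13.2), the investigator must explain missing information (11.1), and consistency checks and queries look for omissions (11.2). A 'Yes' beside a blank grid is the sort of record those checks should catch. The tables are descriptive, the rule is the same in all groups, and a shift of 1.2 points is small beside a 95% interval half-width of about 5 points (1.96 × √(0.4×0.6/350) = 5.1). All of this stands and limits the size. It does not make the rule right, because whatever ungraded 'Yes' records remain are still dropped.

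A reader might infer more than the documents support:

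- **That all solicited rates are biased downward.** Fever is excepted from step 1, so an ungraded 'Yes' and an ungraded 'No' are both Missing and there is no asymmetry. For erythema and swelling from age 12 the sign is not fixed.
- **That the SAP says in words that 'Yes' subjects are excluded.** It does not; this follows from several sections read together.
- **That a 'Yes' with some days recorded None and the rest blank becomes no presence.** Section 4.4.2.1.2 does not say how Missing days enter the maximum, so this is only a possible reading.
- **That the bias is large.** Nothing in the documents supports a high frequency of ungraded 'Yes' records.
- **That reported durations in general are shortened.** Only the overall-days variable depends on ongoing status. The number of days within the solicited period, which is the protocol's endpoint, does not.

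**Conclusion.** The asymmetry holds for solicited reactions other than fever. For injection-site pain, headache, malaise, myalgia and asthenia, the SAP rate is below the rate with known reactors kept whenever at least one ungraded 'Yes' exists and not every subject reacts. The calculation takes the investigator's 'Yes' as correct.

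The size cannot be stated from the documents. Over the assumed range of 1 to 18 such subjects per 350, the shift runs from about -0.2 to -3.3 points at a true rate of 40%, and from about -0.3 to -4.9 points at 10%. The lower end is plausible given the site checks. For erythema and swelling from age 12 no direction can be claimed.

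The ongoing rule is a separate, smaller fault: a missing grade is read as the end of the reaction, which can shorten the overall-days variable only. The primary non-inferiority analyses are untouched. The change is worth making because the rule discards information already collected.

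**What to change.** 1. **Add a step to 4.4.2.1.1 and 4.4.2.1.3.** For the five non-measured symptoms, an investigator 'Yes' with all daily records missing gives presence = Yes and intensity = Missing. The subject stays in numerator and denominator.
2. **Erythema and swelling.** Show 'present, not measured' cases in a separate row or a sensitivity table.
3. **Report the number of ungraded 'Yes' records** by group and injection, so that the reader can judge the effect.
4. **Amend 4.4.2.1.7 for missing grades.** A recorded None on the last day or in the ongoing period still means not ongoing. Otherwise, if either grade is missing, call the reaction ongoing when the other grade is at least 1 and the stop date is after the solicited period. In all remaining cases set ongoing status to Missing, and show the case in the missing category that 4.4.2.1.6 already has.
5. **State in 4.4.2.1.2** how Missing days enter the maximum when some days are graded.

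The cost is SAP wording and a little programming before database lock, with no new data. Reported rates may rise slightly. For any analysis already locked, the count in item 3 and a sensitivity table would be enough.
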